11.1. Appendix 1. PhD Study protocol	

# 1. Study Synopsis

Meniscal tears are common and arthroscopic meniscal surgery is among the most frequently performed procedures in orthopedic surgery. Only one out of ten procedures includes repairs and most operations comprise arthroscopic partial meniscal resections only.

75% of these procedures are performed in those above 35 years of age. As many as 300 persons per 100 000 are going through arthroscopic partial meniscal resections annually. A recent study reveals that the incidence of meniscal procedures performed in Denmark is doubled from year 2000 to 2011.

Most meniscal tears in particular in those 35 years and above, are degenerative tears and may be regarded as the first sign of osteoarthritis (OA). However, degenerative meniscal tears may be present in asymptomatic knees as well and degeneration in meniscal tissue could be looked upon as wrinkles with age and alternatives to surgical treatment should be considered.

A tear in a meniscus with degenerative changes is often associated with preexisting structural changes in the articular cartilage that may represent early-stage osteoarthritis. The menisci have protective properties relative to the joint cartilage surfaces and removal of meniscal tissue leads to degeneration that correlates with the amount of tissue removed. The risk for OA is definitely increased in knees after meniscal resections.

Short- and long-terms studies have shown that exercise therapy improves function and activity level in patients with degenerative meniscal tears whether they have undergone meniscal resections or not. Several studies have shown that arthroscopy is no better than sham surgery, and a recent meta-analysis concludes that there is moderate evidence to suggest that there is no benefit to arthroscopic meniscal debridement for degenerative meniscal tears in comparison with non-operative or sham treatments in middle-aged patients with mild or no concomitant osteoarthritis. Only one recent study reveals that patients treated with meniscal resection combined with instructions for exercise therapy had significant lower pain level after 12 months than patients treated with instruction for exercise therapy only.

Considering the large and assumedly increasing number of patients undergoing surgery, the large number of studies that have shown that meniscal resection increases the risk for knee osteoarthritis, the documented favorable effects of exercise therapy, the scarce documented long-term effects of partial meniscal resection surgery, and the lack of knowledge upon natural development without surgery, there is need for more high quality long-term follow-up randomized controlled studies (RCTs) of the long term effect of exercise therapy versus partial meniscal resection for patients with degenerative meniscal tears.

In this RCT we randomized 140 middle-aged patients (35-60 years) with MRI-verified degenerative medial meniscal tears and no or early knee osteoarthritis (Kellgren-Lawrence (KL) grade of 0, 1 or  $2^{12}$ ) to treatment with either arthroscopic partial meniscal resection or a 12-weeks exercise therapy program^24. The primary outcome is change in knee function measured by KOOS4, a composite of four of the five subscales in the knee specific questionnaire KOOS (Knee injury and Osteoarthritis Outcome Score), from baseline to the 2-year follow-up (Figure 1).

#### 2. Study Objectives and Outcomes

All methods used in this study are described in the PhD study protocol dated April 2012 (Appendix 1). All outcomes were obtained from all participants at baseline and at follow-ups at 3 and 12 months. The 2-year follow-up was performed as a survey included KOOS sent by post and includes all outcomes except the isokinetic muscle strength tests and the performance tests (Table 4). SF-36 was included at all follow-ups but will in this 2-year follow-up study be analyzed only for base line and main outcome at 2 years (see section 2.7).

The 24 months follow-up was finalized in December 2014.

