## 2.2. Secondary Objectives and Outcomes

The secondary objectives are to compare change from baseline to the 2 years follow-up (including all follow-ups) between groups in a range of outcomes, except for isokinetic muscle strength and functional performance, for those the endpoint is 1-year follow-up.

Secondary outcomes differ from exploratory outcomes, because secondary outcomes will possibly enable clinical interpretations; not only be explanatory or hypothesis generating. Secondary outcomes give support to the primary outcome and will contribute to better interpretation and eventually more knowledge. Since secondary outcomes only are seen as supportive for the primary outcome, multiplicity is not considered to be a problem and not statistically corrected for.

These outcomes are:

1) The five subscales of KOOS in hierarchic sequence: a. QOL b. Sport/Rec. c. Pain d. Symptoms e. ADL.

2) Functional performance: a. The one-leg hop test b. The 6 meter timed hop test c. The kneebending test

3) Isokinetic muscle strength: a. Quadriceps strength b. Hamstrings strength

4) SF-36: Physical component summary (PCS) and mental component summary (MCS)

5) Global knee rating (much better – better– unchanged – worse – much worse)

7) To analyze the number needed to treat (NNT), based on a 15% difference in change in KOOS between groups from baseline to the 2 years applied in recent studies in similar patient populations, (see section 2.7.1.).

8) The health economic utility instruments EQ-5D index including EQ-5D VAS is included in the baseline and follow-up surveys. This will not be a part of this 2-year follow-up, but will be published later in a separate paper (see section 2.5.).

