## 2.7. Specification of Endpoints

#### 2.7.1. Primary Endpoint

The trial is designed as a superiority trial, i.e. we expect that one of the treatment groups will improve more than the other group in the primary outcome  $KOOS_4$  from baseline to the primary endpoint after 2 years. Thereby, the primary endpoint is based upon the between-group difference in change in  $KOOS_4$ .

The primary analysis of the primary outcome (KOOS4) will be analyzed in an intention-totreat (ITT) analysis. It implies that for all patients randomized to one treatment, should be analyzed according to the treatment to which the patient was allocated, irrespective of whether they received this or some other treatment, or no treatment at all (Figure 2). The purpose of this ITT principle is to preserve the theoretical basis for the validity of the statistical results, specifically by eliminating the possibility that patients with known or unknown prognostic factors are systematically selected to a treatment.

The *ITT population* is equal to all patients randomized to the two treatment arms, and the dataset is equal to the "all patients randomized set" (APRS).

Missing values due to patients' absence from follow-ups or withdrawal from the study are not uncommon in clinical trials. Several approaches are described for handling missing data in the ITT analysis, and among them "last observation carried forward" (LOCF) (the last observed outcome is regarded as the final outcome), multiple imputation (MI) (stochastic technique which depends on model-based imputation of multiple values for each missing observation) and mixed model (MM) analysis. A MM analysis includes all patients with at least one baseline or follow-up value, and includes both fixed and random factors. The MM method is shown to have higher statistical precision in analyzing data from an RCT, than LOCF or MI methods. Therefore, MM method is chosen for the analysis of the primary outcome in this trial.

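### SF-36 was collected at four time points but is to be analysed from two, which conflicts with Section 2.2 and leaves no rule for patients without a 2-year value

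*SAP*

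**What the plan says.** - **Collection.** SAP Section 2: "SF-36 was included at all follow-ups". The same section describes the last contact: "The 2-year follow-up was performed as a survey included KOOS sent by post".
- **Restriction.** Section 2 continues that SF-36 "will in this 2-year follow-up study be analyzed only for base line and main outcome at 2 years" and refers the reader to Section 2.7. Sections 2.7.1 and 2.7.2 do not mention SF-36, so the pointer leads to no rule.
- **General rule for secondary outcomes.** Section 2.2: "The secondary objectives are to compare change from baseline to the 2 years follow-up (including all follow-ups) between groups". The only exemptions are isokinetic strength and functional performance, whose endpoint is 1 year. SF-36 (PCS and MCS) is item 4 on the list that follows and is not exempted.
- **Analysis method.** Section 5.2 gives secondary outcomes ANOVA in the ITT population, or non-parametric tests if assumptions fail. It names no method for missing values.
- **Primary outcome, for contrast.** Section 2.7.1 discusses missing follow-up and says "A MM analysis includes all patients with at least one baseline or follow-up value". It then concludes: "Therefore, MM method is chosen for the analysis of the primary outcome in this trial". The code in Section 5.1 is a repeated-measures model of change in KOOS4 by visit.

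**The concern.** Two sections of the SAP give different instructions for the same endpoint, and Section 7 makes the SAP the statistician's working document. A statistician who follows Section 2 leaves out the 3- and 12-month SF-36 scores. With only baseline and 2 years in the data set and no missing-data rule in Section 5.2, a patient without the 2-year questionnaire has no change score and cannot inform the group contrast.

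Three things are at stake:

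- PCS and MCS are meant to support the primary result, yet they would in effect rest on fewer patients than KOOS4.
- Some precision is given up, although the data already exist.
- The SF-36 contrast loses protection against one form of non-response: the kind related to how patients were doing at 3 and 12 months. The last contact was by post and participants were not blinded (Section 3.2), so arm-related non-response is conceivable. The SAP gives no evidence that it occurred.

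**Working it through.** **1. The plan's own figure.** The only sample size is for KOOS4 (Section 3.1): 2 × 15² / 10² × 10.5 = 47.25, so 48 per group. With 15% dropout, 47.25 / 0.85 = 55.6, so 56 per group and 112 in total. This reproduces and is not affected by the point. No figure is given for SF-36. The input needed here is the 15% dropout.

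**2. Patients affected.** Randomised: 140 (Section 1). Expected without a 2-year value: 140 × 0.15 = 21. Remaining: 140 − 21 = 119, or about 59.5 per arm.

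**3. Possible bias.** The SAP gives no SF-36 SD, visit correlations or dropout mechanism, so these are assumptions:

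- SD 10, and equal correlation ρ between all four visits
- no true group difference
- 15% missing at 24 months
- where non-response is informative, an odds ratio of 2.7 per SD of the score

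The two-point analysis is ANCOVA of the 24-month score on baseline in responders, simulated with 300,000 patients per arm. Absolute bias in points:

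| 2-year non-response depends on | ρ = 0.4 | ρ = 0.6 | ρ = 0.75 |
|---|---|---|---|
| nothing (random) | 0.03 | 0.03 | 0.01 |
| 12-month score, same way in both arms | 0.01 | 0.01 | 0.02 |
| baseline only, opposite ways by arm | 0.04 | 0.01 | 0.00 |
| 12-month score, one arm only | 0.26 | 0.32 | 0.22 |
| 12-month score, opposite ways by arm | 0.68 | 0.67 | 0.50 |

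The first three rows are zero within simulation error. Predicting the 24-month score within arm from baseline, 3 and 12 months (a stand-in for a mixed model under missing at random) gives at most 0.06 in every cell.

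**4. Bias against sampling error.** The standard error of the two-point contrast is about 10 × √(1 − ρ²) × √(2/59.5), and √(2/59.5) = 0.183.

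- ρ = 0.4: 9.17 × 0.183 = 1.68
- ρ = 0.6: 8.00 × 0.183 = 1.47
- ρ = 0.75: 6.61 × 0.183 = 1.21

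The opposite-direction bias is therefore 0.68/1.68 = 0.40, 0.67/1.47 = 0.46 and 0.50/1.21 = 0.41 standard errors.

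**5. Sensitivity to the correlation pattern.** Suppose baseline correlates 0.5 with each follow-up, the follow-ups correlate 0.5 to 0.8 with each other, about 15 to 20% are missing, and dropout runs in opposite directions. Bias is then 0.36 to 0.83 points at an odds ratio of about 1.65, and 0.69 to 1.57 at about 2.7.

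**6. Precision if dropout is random.** Using all visits multiplies the standard error by about √(1 − m·R²). Here m is the fraction missing. R² is the share of the 24-month variance left after baseline that the 3- and 12-month scores explain. With baseline correlation b and follow-up correlation r, p = (r − b²)/(1 − b²) and R² = 2p²/(1 + p). For b = 0.5 and m = 0.15:

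- r = 0.5: p = 0.333, R² = 0.167, factor √(1 − 0.025) = 0.987
- r = 0.8: p = 0.733, R² = 0.621, factor √(1 − 0.093) = 0.952

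The gain is about 1 to 5%.

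**The case against.** **The exclusion is not written down.** Section 5.2 names the ITT population, and Section 2.7.1 defines that as everyone randomised. This stands: the SAP has no complete-case rule, and the loss of patients is inferred from the two-time-point restriction together with the missing rule. But naming a population does not supply a value for someone who has none, so the practical effect is as described unless an unstated imputation is used.

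**Section 2 may only limit what is reported.** Table 2 shows SF-36 at baseline and Table 4 shows it at 2 years, which fits that reading. It cannot be ruled out. The wording, however, restricts the analysis. If reporting was meant, the replacement sentence below says so.

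**The specific statement may govern the general one.** The phrase in Section 2.2 covers a range of outcomes, while Section 2 makes an open, specific choice for one instrument. That is fair, but Section 2.2 lists its exemptions and SF-36 is not among them.

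**The mixed model was never promised for SF-36.** Correct. Section 2.7.1 chooses it for the primary outcome only. Extending it is a recommendation that borrows the SAP's own argument; the SAP does not break a commitment.

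**The missing-data gap affects every secondary outcome.** Also correct. SF-36 stands out because it alone is expressly cut to two time points although interim scores were collected and its endpoint is 2 years.

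**A reader might infer that the SF-36 result will be biased, by as much as 1.6 points.** The documents do not support that. Nothing in them shows arm-dependent non-response, and 1.6 needs opposite-direction dropout, the steepest odds ratio and the highest follow-up correlation tried.

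**Conclusion.** The point holds in a limited form. Sections 2 and 2.2 disagree on which SF-36 assessments are analysed, the pointer to Section 2.7 does not resolve it, and Section 5.2 has no missing-data rule to fall back on. About 21 of 140 patients would in effect add nothing to the 2-year SF-36 contrast if dropout is the planned 15%; the actual figure is not in the SAP.

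Bias is conditional on non-response that depends on interim scores, beyond baseline, differently by arm. It is then illustratively 0.2 to 0.7 points on an assumed SD of 10, below half a standard error, and about 0 otherwise. Stronger assumptions give more, as shown above. The interim scores remove the bias only if data are missing at random given the observed scores; they do not help if non-response depends on the unseen 2-year state. With uninformative dropout the loss is 1 to 5% in standard error.

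The consequence is small. SF-36 is a supportive secondary outcome, no stated figure changes, and the KOOS4 analysis already uses all visits.

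**What to change.** Replace the restriction in Section 2 with a sentence such as: *All SF-36 assessments (baseline, 3, 12 and 24 months) enter the same longitudinal mixed model as KOOS4; only baseline values and the 24-month between-group difference are reported.* Add a matching clause in Section 5.2 so that its ANOVA or non-parametric rule does not contradict this for PCS and MCS, and drop or correct the pointer to Section 2.7.

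The cost is slightly more modelling: the code in Section 5.1 run twice more, with PCS and MCS in place of KOOS4. The data are already collected, and Tables 2 and 4 stay as they are.

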#### 2.1. Primary Objective and Outcome

The primary objective is to compare difference in change in knee function measured by KOOS4 from baseline to the 2-year follow-up (including follow-ups at 3 months and 1 year) between patients randomized to exercise therapy or arthroscopic partial meniscal resections. The reason for choosing this primary endpoint is as follows:

The KOOS is a knee-specific instrument, developed to assess the patients' opinion about their knee and associated problems. The KOOS evaluates both short-term and long-term consequences of knee injury. The KOOS subscales has previously been found reliable and are validated for patients with a range of knee injuries including those having knee arthroscopy and those with knee OA.

The KOOS holds 42 items in 5 separately scored subscales; Pain, other Symptoms, Function in daily living (ADL), Function in Sport and Recreation (Sport/Rec), and knee-related Quality of Life  $(QOL)^{26}$ . Each item in KOOS is scored from 0-4 on a Likert scale. Subscale scores are given separately (see www.koos.nu for user's guide and scoring) ranging from 0 (worst) to 100 (best). In this study, each subscale except ADL will be calculated according to the instructions in the user's guide and the composite KOOS4 will be calculated giving each subscale equally large impact on the KOOS4 score using this formula:

KOOS4 = (KOOS Pain + KOOS Symptoms + KOOS Sport/Rec + KOOS QOL)/4

An average KOOS score derived from any number of calculated subscales scores can be used as primary endpoint in an RCT, if defined a priori. However, since  $KOOS_4$  has not been subjected to psychometric validation, they are intended for statistical purposes only and cannot be interpreted clinically. The individual KOOS subscales must be analyzed as secondary outcomes to enable clinical interpretation of the contributions of each subscale of the KOOS score.

One reason for choosing a composite KOOS score as the primary endpoint is to avoid issues with *multiplicity*. Another reason is to avoid bias between groups because *group belongingness* only may favor scores in some KOOS subscales. The third reason is that especially the KOOS subscale ADL has *low effect size* and is actually not optimal for measuring differences in knee function when analyzed in this patient population. The assumed group belongingness bias and effect size difficulties will be discussed below:

Group belongingness: Bias between the patient groups will certainly occur as a consequence of the different treatment interventions (exercises versus surgery). It is reasonable to suggest

that the context for each group at follow-ups is different due to experiences and knowledge the patients have acquired during either surgery or exercise therapy. This may have an effect on the change in scores. Gauffin et al has shown higher KOOS pain scores (less pain) after 12 months in patients that have gone through arthroscopy in addition to exercise, compared to patients that had exercise only. This may in fact be a result from placebo effect of the surgery and the patients' expectations of good results.

In a previously published study by our group based on the 20 first subjects in the exercise therapy group of the OMEX trial, patients scored statistically and clinically significant higher in all KOOS subscales after 12 weeks exercise therapy. The highest effect sizes (1.7 and 1.7) were seen in the subscales Sport/Rec and QOL, compared to the lower effect sizes in the subscales ADL, Pain and Symptoms (1.1, 1.5 and 0.5 respectively). This may actually reflect an unintended side effect of the exercise intervention: During the exercises, the patients have had frequent contact with the physiotherapist who assumedly have given instructive information and taught the patients that physical activity is not dangerous in spite of the experience of pain. Thereby, the patients have the courage to get more physical active and this may influence on the changes in knee related quality of life, as well, and changes in the subscales QOL and Sport/Rec.

Therefore, the group belongingness itself may have influence on the self-reported follow-up scores.

Effect sizes: In the above mentioned study by Stensrud et al, the smallest effect sizes after exercise therapy were found for the KOOS subscales Symptoms and ADL  $(0.5 \text{ and } 1.1)^{24}$ . This is analogue to Herrlin et al's study of patients having arthroscopy and exercises compared to exercises only, where the smallest changes in scores were seen in the subscales Symptoms and ADL. Likewise, also in Gauffin et al's study, the smallest changes were seen in the subscales Symptoms and ADL, and there were no significant differences between the treatment groups for the subscales Symptoms and ADL in the per-protocol analyses of mean scores at 12 months, but a significant difference in favor of the surgery group for the subscale Symptoms in the as-treated-analysis.

Therefore, the KOOS subscales Symptoms and ADL seems to have low effect sizes and only small, if any, differences between groups are expected.

Another argument for excluding the subscale ADL from the composite score: This patient population is middle-aged (35-60 years), the patients have no serious comorbidities (due to the inclusion and exclusion criteria) and it is reasonable to suspect that the patients at baseline actually not have serious problems with usual activities of daily life, even though they experience knee pain and functional limitations. Thereby, the KOOS subscale ADL could be considered less valid and leave less room for improvement in this population. On the other hand this is an early OA group, and their baseline score is about 50-60. I think this paragraph could be omitted since this the speculations are not substantiated by facts.

Therefore, we have chosen not to use a single subscale as the primary outcome of this RCT, but to use a composite KOOS score; the KOOS4, without the subscale ADL.

## 2.2. Secondary Objectives and Outcomes

The secondary objectives are to compare change from baseline to the 2 years follow-up (including all follow-ups) between groups in a range of outcomes, except for isokinetic muscle strength and functional performance, for those the endpoint is 1-year follow-up.

Secondary outcomes differ from exploratory outcomes, because secondary outcomes will possibly enable clinical interpretations; not only be explanatory or hypothesis generating. Secondary outcomes give support to the primary outcome and will contribute to better interpretation and eventually more knowledge. Since secondary outcomes only are seen as supportive for the primary outcome, multiplicity is not considered to be a problem and not statistically corrected for.

These outcomes are:

1) The five subscales of KOOS in hierarchic sequence: a. QOL b. Sport/Rec. c. Pain d. Symptoms e. ADL.

2) Functional performance: a. The one-leg hop test b. The 6 meter timed hop test c. The kneebending test

3) Isokinetic muscle strength: a. Quadriceps strength b. Hamstrings strength

4) SF-36: Physical component summary (PCS) and mental component summary (MCS)

5) Global knee rating (much better – better– unchanged – worse – much worse)

7) To analyze the number needed to treat (NNT), based on a 15% difference in change in KOOS between groups from baseline to the 2 years applied in recent studies in similar patient populations, (see section 2.7.1.).

8) The health economic utility instruments EQ-5D index including EQ-5D VAS is included in the baseline and follow-up surveys. This will not be a part of this 2-year follow-up, but will be published later in a separate paper (see section 2.5.).

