Treatment effect will be determined as difference between groups in change in the primary outcome KOOS4 from baseline to the 2-year follow-up. Since KOOS contains the full and original version of the Western Ontario and McMaster Universities Osteoarthritis Index (WOMAC), it has been usual to apply a minimal important change (MIC) of 10 points, which has been demonstrated for WOMAC. Recent studies in OA patient populations have applied a MIC of 15%. However, percentage change from baseline is not recommended as an outcome in controlled trials, since it has low statistical power, is highly sensitive to changes in variance and fails to protect from bias in the case of baseline imbalance.

We acknowledge that MIC is dependent on context factors such as population, intervention, and time to follow-up. In this trial, a possible bias may be a result of the different interventions (see section 2.1.) and this may affect the scores in the different KOOS subscales different in the two treatment groups, and thereby the change in KOOS4 may differ in the two groups as a result of the bias alone. Therefore, in the between-group analyses, the MIC is dubious and of poor value. On the contrary, in the within-group analyses, it is still reasonable to assess a 10-point difference as MIC.

Superiority will be tested using the two-sided 95% confidence interval (CI) of the mean change in  $KOOS_4$  between the two treatment groups.

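### The NNT rests on a 15% between-group difference in KOOS change, which classifies no patient and which the section it cites argues against

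*SAP*

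**What the plan says.** Section 2.2, item 7, lists the NNT among the secondary outcomes, "based on a 15% difference in change in KOOS between groups" from baseline to 2 years. It attributes the 15% to recent studies and refers to section 2.7.1. The score is given only as KOOS, without saying whether KOOS4 or one of the five subscales is meant.

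Section 2.7.1 contains no responder definition and no NNT method. It makes four remarks that bear on item 7:

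- Recent studies in osteoarthritis, the same two references as in item 7, "have applied a MIC of 15" per cent.
- However, "percentage change from baseline is not recommended as an outcome in controlled trials, since it has low statistical power". Sensitivity to variance and lack of protection against baseline imbalance are given as further reasons.
- Because the two interventions may bias the scores differently, "in the between-group analyses, the MIC is dubious and of poor value".
- By contrast, "in the within-group analyses, it is still reasonable to assess a 10-point difference as MIC".

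Section 5.2 offers ANOVA or non-parametric tests for secondary endpoints and does not mention responders. Table 4 has no row for a responder proportion or an NNT.

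**The concern.** Item 7 fixes the NNT on the wrong kind of quantity. A difference between two arms in change describes groups. It does not say which patients responded, and without that there are no proportions to subtract and invert.

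The statistician must therefore supply a criterion, and the section cited for help speaks against the one given on two counts: it is a percentage, and it is a minimal important change applied between groups. Section 7 makes the SAP the statistician's work description, so this choice would be made during analysis. Section 2.2 expects secondary outcomes to support clinical interpretation, and an NNT is a clinical statement. Its value should not depend on a cut-off picked once the data are in hand.

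**Working it through.** **Plan's own figure.** The SAP states no NNT and no responder rates, so there is none to reproduce. The SD and difference used below come from the sample size in section 3.1, which does reproduce: 2 × 15² / 10² × 10.5 = 47.25, rounded up to 48 per group; 47.25 / 0.85 = 55.6, rounded up to 56 per group; 2 × 56 = 112.

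**Step 1: what an NNT needs.** NNT = 1 / (p₂ − p₁), where each p is the proportion of an arm whose individual change reaches a cut-off c. Item 7 supplies no c.

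**Step 2: candidate cut-offs.**

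- 15% of the patient's own baseline. Section 2.1 says of these patients that "their baseline score is about 50-60". The sentence stands in the paragraph on the ADL subscale, so using it for another score is an assumption. It gives 0.15 × 50 = 7.5 and 0.15 × 60 = 9 points. At other assumed baselines, 0.15 × 40 = 6 and 0.15 × 70 = 10.5. The cut-off is below 10 points whenever baseline is under 10 / 0.15 = 66.7.
- 10 points, the MIC that section 2.7.1 keeps for within-group analyses.
- 15 points on the 0–100 scale, if the per cent sign is read as points.

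**Step 3: effect on the NNT.** Assume individual changes are normal with SD 15 in both arms (section 3.1 gives 15; taking it as the SD of change is an assumption) and a true difference of 10 points. Let m be the mean change in the reference arm, which the SAP does not give and is assumed. Then p₁ = Φ((m − c)/15) and p₂ = Φ((m + 10 − c)/15).

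| m (assumed) | c | p₁ | p₂ | p₂ − p₁ | NNT |
|---|---|---|---|---|---|
| 15 | 7.5 | 0.691 | 0.878 | 0.187 | 5.35 |
| 15 | 9 | 0.655 | 0.857 | 0.202 | 4.96 |
| 15 | 10 | 0.631 | 0.841 | 0.211 | 4.74 |
| 15 | 15 | 0.500 | 0.748 | 0.248 | 4.04 |
| 25 | 7.5 | 0.878 | 0.967 | 0.088 | 11.33 |
| 25 | 9 | 0.857 | 0.958 | 0.102 | 9.85 |
| 25 | 10 | 0.841 | 0.952 | 0.111 | 9.02 |
| 25 | 15 | 0.748 | 0.909 | 0.161 | 6.20 |

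The NNTs come from unrounded proportions. With m held fixed, the cut-off alone moves the NNT by a factor of 5.35 / 4.04 = 1.3 at m = 15 and 11.33 / 6.20 = 1.8 at m = 25. Comparing across values of m would mix in the assumed reference-arm change, which is not due to the wording of item 7. The rows for 7.5 and 9 points apply one cut-off to everyone; a true own-baseline rule would mix cut-offs within each arm.

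**The case against.** **The intended meaning can be guessed.** Item 7 takes its 15% from the same references that section 2.7.1 describes as using a 15% MIC, so the authors may have meant patients who improve by at least 15%. That is a fair guess, and under it an NNT can be computed. A reader might infer that no reading of item 7 is workable; that goes too far. What stands is that the text states a between-group criterion, that more than one repair is possible, and that they give different answers. Section 2 refers to the PhD protocol (Appendix 1) for methods. That document is not at hand, and a definition there would still have to be reconciled with item 7.

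**Section 2.7.1 is mainly about the primary effect.** This is true. A reader might infer that the SAP rejects 15% outright. Its words are milder (not recommended; dubious), and 15% is never withdrawn for the NNT. The reasons given apply to item 7 all the same.

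**Ten points is not a ready-made replacement.** A reader might infer that the SAP endorses 10 points as a patient-level threshold. It says within-group, takes the figure from WOMAC, and warns that a MIC depends on context. Section 2.1 also says KOOS4 cannot be interpreted clinically, which sits badly with a KOOS4 responder.

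**A fixed cut-off also depends on baseline.** On a 0–100 scale nobody starting above 90 can gain 10 points, just as nobody starting above 100 / 1.15 = 87 can gain 15%. An absolute cut-off is therefore no full cure for baseline imbalance. This objection stands and is the reason for adjusting for baseline.

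**The unnamed score is a smaller matter.** The reference to section 2.7.1 suggests KOOS4, but given section 2.1 the score should be named.

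**Conclusion.** The concern holds for one secondary outcome. Item 7 bases the NNT on a group-level quantity from which no NNT follows, no patient-level responder definition appears in the SAP, and the cited section argues against the criterion. Choosing among plausible cut-offs changes the NNT by a factor of about 1.3 to 1.8 in the illustrations, which rest on normal changes, SD 15, a true 10-point difference and an assumed reference-arm mean change of 15 or 25.

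A reader might infer that the trial's main conclusion is exposed, or that the NNT will be its headline figure. The documents support neither. The NNT is one item in a list described as supportive and has no row in Table 4. The KOOS4 mixed model and the sample size do not use it.

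**What to change.** Before the allocation code is broken, replace the criterion in section 2.2, item 7, with these elements:

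- **Score.** Name it. Either use a KOOS subscale or, if KOOS4 is kept, label the resulting NNT as supportive only, in line with section 2.1.
- **Responder.** Define response as an absolute improvement in that score from baseline to 24 months. Ten points is the only absolute MIC the SAP retains; state its use for individual patients as an assumption.
- **Missing data.** Say how a patient without a 24-month score is handled. The mixed model chosen for KOOS4 does not by itself classify such a patient.
- **Estimate.** Report the ITT difference in responder proportions with its 95% CI, preferably adjusted for baseline score. Derive the NNT and its interval from that difference, and say so when the CI includes zero, since the NNT interval is then not a single finite range.
- **Table 4.** Add a row for the responder proportions, their difference and the NNT.

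The cost is a few sentences and one table row. No new data are needed.
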